4.1 General Principles

The statistical evaluation will be performed by using the software package SAS release 9.2 or higher (SAS Institute Inc., Cary, NC, USA) and other specialized software can be used for sensitivity analysis. All variables will be analyzed by descriptive statistical methods. The number of data available and missing data (nmiss), mean, standard deviation, minimum, quartiles, median, and maximum will be calculated for metric data. Frequency tables will be generated for categorical data.

As children were to be randomized also to standard of care before Protocol Amendment 4 comes into effect, data from these children will be presented separately in tables and listings where applicable.

The analysis datasets (ADS) standards for Xarelto will be applied.

4.2 Handling of Dropouts

For all children, visits are scheduled at regular time points (see study flow chart on Figure 1-1 of the Integrated Protocol and Local Amendments). Enrolled children who are not treated or those with premature discontinuation of study drug will at least be seen at the end of the study treatment period. During all contacts, the treatment and clinical course of the child will be evaluated. Children with suspected efficacy or safety outcomes will undergo confirmatory testing as per standard of care. Blood samples for PK/PD will be taken at defined time points (see study flow chart on [Figure 1-1](#) of the Integrated Protocol).

For further details about collecting data from children who prematurely discontinue study medication see Integrated Protocol Sections [3](#) and [7.10](#).

4.3 Handling of Missing Data

All missing or partial data will be presented in the subject data listing as they are recorded on the Case Report Form (CRF).

The number of subjects who prematurely discontinue the study treatment and/or the study for any reason, as well as the reasons for premature discontinuation of study treatment will be reported for the treatment period. Days to end of study treatment and days to last visit will be listed for subjects who prematurely terminate study treatment.

Baseline characteristics will be summarized descriptively by non-completers (prematurely discontinuation the study treatment and/or the study respectively) versus completers.

The number of missing repeat imaging tests, number of missing laboratory values at baseline and at visit 4, number of missing weight values will be displayed by means of descriptive statistics for the rivaroxaban group and separately for children who randomized to standard of care before Protocol Amendment 4 comes into effect.

General rules

When appropriate, the following rules will be implemented so as not to exclude subjects from statistical analyses due to missing or incomplete data:

- **Index thrombosis**
For cases where start month and year are reported but day is missing, impute it with the complete start date of pre-treatment or if no complete start date is available, with 15. For cases where months and/or year is missing impute it with the complete start date of pre-treatment or if no complete start date is available, no imputation will be done.
- **Start and stop dates for pre-treatment of index events**
Missing start date will be imputed as max [(01, available month or 01, available year or IxRS year) and available complete date of index event]. Missing stop dates will be imputed as date of IxRS assignment.
- **Safety and efficacy clinical outcomes, adverse events**
For cases where start month and year are reported but day is missing, impute the maximum of (date of IxRS assignment, first date of study medication, 01.month.year). For cases where only start year is reported, impute the maximum of (date of IxRS assignment, first date of study medication, 01.01.year), but not later than death date if the patient died.
- **Study medication start date**
If the start day of study medication is missing then the start date will be imputed as the maximum of (date of IxRS assignment, 01.month.year). Otherwise if start month is also missing then the start date will be imputed with the date of IxRS assignment. If start date and time is recorded as earlier than IxRS assignment and cannot be clarified, date and time of IxRS assignment will be used for the statistical analysis.

Study medication stop date

If stop date is missing and there is an adverse event with action taken ‘study medication discontinued permanently’ then the stop date of study medication will be imputed by the start date of that adverse event.

Otherwise if the stop day is missing, but the stop month and stop year are available then the stop date will be imputed as minimum of [(15, month, year) and the last study visit date before the observational visit and death date]. If the stop day and month are missing then the stop date will be imputed as minimum of [the last study visit date before the observational visit and death date].

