7.4 Safety analysis - amended

All safety analyses will be performed on the SAS population. The analysis will primarily focus on bleeding that occurred during or within 2 days after stop of study treatment. Bleeding events observed later will be described separately.

Individual listings of major and clinically relevant non-major bleeding will be provided. The incidence of bleeding will be summarized descriptively. If a sufficient number of bleeding events is observed, factors which potentially influence the occurrence of bleeding will be assessed by appropriate statistical procedures.

Quantitative data will be described by the summary statistics and will be presented descriptively for the original data as well as for the difference to baseline. Frequency tables will be provided for qualitative data.⁴⁸

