6.2 Bleeding analysis

All bleeding analyses will be performed on the safety analysis set based on the outcomes confirmed by the CIAC. Bleeding events that occurred during study treatment or within 2 days after stop of study medication (i.e. treatment-emergent) will be summarized. Bleeding events observed more than 2 days after stop of study medication will be described separately. Individual listings of major and clinically relevant non-major bleeding events will be provided.

Incidence proportions (number of children with outcome by number of children at risk at start of study medication) will be presented for the primary safety outcome, for major bleedings, for all confirmed bleedings and components for pooled data and for each age stratum and by baseline presentation of venous thrombosis for the rivaroxaban group and for the standard of care group (randomized before Protocol Amendment 4) separately.

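### A missing stop day for study medication is imputed as the 15th or earlier with no floor at first dose, so the stop can precede the start and on-treatment bleeds can leave the primary window

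*SAP*

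**What the plan says.** SAP 4.3 (Handling of Missing Data) gives three rules for a missing stop date of study medication, in order.

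1. If an adverse event led to permanent discontinuation, "the stop date of study medication will be imputed by the start date of that adverse event".
2. Otherwise, if only the day is missing, "the stop date will be imputed as minimum of [(15, month, year) and the last study visit date before the observational visit" or the death date, whichever is earliest.
3. If day and month are both missing: "If the stop day and month are missing then the stop date will be imputed as minimum of [the last study visit date"; as in rule 2, this means the final visit ahead of the post-treatment contact, with the death date used if earlier.

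The neighbouring rules have a lower bound. For a study medication start with a missing day, "the start date will be imputed as the maximum of (date of IxRS assignment, 01.month.year"). For outcomes and adverse events with a missing day, "impute the maximum of (date of IxRS assignment, first date of study medication, 01.month.year").

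The stop date closes the main safety window. Protocol 7.4 states: "The analysis will primarily focus on bleeding that occurred during or within 2 days after stop of study treatment". SAP 6.2 adds: "Bleeding events observed more than 2 days after stop of study medication will be described separately". The incidence there is the "number of children with outcome by number of children at risk at start of study medication".

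**The concern.** Every term in rule 2 is an upper bound, so the imputed stop can fall before the first dose. Even when it does not, fixing the day at the 15th or earlier closes the window too soon for any child who really stopped more than 2 days after the 15th.

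A bleed in the gap leaves the treatment-emergent numerator, while the child stays in the denominator, which is fixed at start of treatment. The observed incidence of the primary safety outcome is then too low.

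The same date feeds three other places: the treatment-emergent adverse event window (SAP 6.5.2), the compliance period of stop minus start plus 1 day (SAP 4.5.2.1), and the 25-day threshold of the per protocol set (SAP 5.1). The main efficacy analysis in SAP 6.3 is unaffected, because it runs to 30 days after assignment whatever the actual stop date.

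**Working it through.** The plan states no figure for this rule, so there is none to reproduce.

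**Inputs.** Rule 2 of SAP 4.3; a 30-day course (Protocol 5.3); a window ending at stop + 2 days (Protocol 7.4, SAP 6.2); Visit 4 still held after early discontinuation (Protocol 6.5), so the last-visit term is normally about Day 30; 20 children (SAP 9.1). Assumptions: all 365 start dates of a non-leap year equally likely, no deaths, Visit 4 at Day 30. Everything is conditional on a missing stop day with month and year known and rule 1 not applying.

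**Single case.** Start 20 March, true stop 28 March.
- Imputed stop = min(15 March, Visit 4) = 15 March.
- Duration = 15 - 20 + 1 = -4 days.
- The window closes on 17 March, before the first dose, so no on-treatment bleed can fall inside it.

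**Stop before start.** This needs a start after the 15th and a stop in the same month, so at most 16 days of treatment (16th to 31st). A month with n days after the 15th has n(n+1)/2 such start/stop pairs:
- 31-day months (n = 16): 136 each, 7 × 136 = 952
- 30-day months (n = 15): 120 each, 4 × 120 = 480
- February (n = 13): 91
- Total 952 + 480 + 91 = 1,523

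For stops on Days 1-26, equally weighted, there are 365 × 26 = 9,490 combinations, and 1,523 / 9,490 = 16.0%. Spread over Days 1-29 it is 1,523 / 10,585 = 14.4%. From Day 17 onward it cannot occur.

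**30-day completers.** True stop = start + 29 days, so across the year each calendar day is a stop day once.
- Stop imputed early at all (true stop after the 15th): (365 - 12 × 15) / 365 = 185 / 365 = 50.7%; mean 1,523 / 185 = 8.2 days early, maximum 16.
- More than 2 days early, the share that matters given the 2-day extension: (365 - 12 × 17) / 365 = 161 / 365 = 44.1%.
- On-treatment days outside the window: (7 × 105 + 4 × 91 + 66) / 365 = 1,165 / 365 = 3.2 of 30 on average, maximum 14. Example: 1 to 30 March is imputed as 15 March, so bleeds from 18 to 30 March are moved out.
- Imputed duration below 25 days (more than 5 days early): (365 - 12 × 20) / 365 = 125 / 365 = 34.2%.
- Stop before start: none.

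**Effect of one child.** If a child's only qualifying bleed is moved out, the incidence changes from 1/20 = 5% to 0/20 = 0%.

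**Alternative rules, early stops on Days 1-26.** Mean distance from the true stop is 7.3 days under rule 2 and 30 - 13.5 = 16.5 days under rule 3. Taking the latest possible date, max(first dose, min(last day of reported month, last visit before the observational visit, death date)), never falls before the true stop. It overshoots by 10.8 days on average, by more than 7 days in 62% of combinations, and by up to 29.

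**The case against.** Several counter-arguments have force.

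- **The trigger is unlikely.** Parents must record the exact time of the last dose before Visit 4 (Protocol 6.4), the site documents it again (6.5), and dosing times go into the eCRF (6.12). A completer with only the stop month known would contradict several required records. This stands, though the Visit 4 sampling that depends on dose timing is not required after permanent early discontinuation, which is where a stop before the start can arise.
- **The adverse event branch comes first.** A bleed recorded as the event that caused permanent discontinuation sets the stop date itself and stays in the window. This stands. Bleeds with temporary or no interruption, and stops for other reasons, are not covered.
- **Nothing is lost from the report.** Major and clinically relevant non-major bleeds are listed individually and later bleeds are described separately. There is no hypothesis test or decision rule. This stands: the effect is on the headline proportion, not on disclosure.
- **General safeguards.** SAP 4.3 applies its rules where appropriate, and SAP 4.6 and 5.1 provide for a data review. A negative duration would be noticed among 20 children, but neither supplies a floor, and a stop 10 days early in a completer looks plausible.

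A reader might infer that knowing the month always gives a worse date than not knowing it, since rule 3 falls back on the last visit. The rules do not bear this out: knowing the month can only keep the date or move it earlier, which hurts completers, but for early stoppers it more than halves the mean error (7.3 against 16.5 days). A reader might also infer that the rule always shortens the window. It does not: among early stops, 12 × 14 / 365 = 46% have a true stop before the 15th and an imputed stop that is too late.

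**Conclusion.** The rule is wrong as written, because it can produce a stop before the first dose, and it should be corrected. Given a missing stop day, this happens in 16% of start/stop combinations for equally weighted stops on Days 1-26. In 30-day completers it does not happen, but the window closes more than 2 days early for 44% of start dates. One child moved out of the numerator is worth 5 percentage points.

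The percentages rest on uniform start dates, Visit 4 at Day 30, no deaths and, for early stops, equal weights. The documents give no rate of missing stop days and suggest that they are rare, so the effect on the reported incidence may be zero. The documents do not support a claim that the primary bleeding incidence will be materially biased.

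**What to change.** 1. Add a floor to the stop date rules in SAP 4.3: imputed stop = max(first dose date, date from the current rule). This costs one sentence and has no evident downside. It removes impossible dates but leaves the completers' 44% unchanged.

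2. For the bleeding and adverse event windows only, use max(first dose date, min(last day of reported month, last study visit before the observational visit, death date)), or report this as a sensitivity analysis beside the current rule with the floor. In the enumeration no on-treatment bleed then leaves the window.

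The second step has a real cost. After an early stop it lengthens the window by about 11 days on average and up to 29. Because further anticoagulation is at the investigator's discretion (Protocol 3 and 7.10), it may count bleeds on later anticoagulants as treatment-emergent. Used for compliance, it would inflate the volume due and so deflate the ratio, and SAP 5.1 excludes children below 50% from the per protocol set. Compliance and per protocol membership should therefore not use the latest-date rule.

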4.4 Interim Analyses and Data Monitoring

No interim analysis will be performed.

An independent Data Monitoring Committee (DMC) will monitor the children’s safety and give recommendations to the steering committee. The DMC has the responsibility to provide the steering committee and the sponsor with recommendations related to the protection of the children’s safety, including stopping recruitment and study treatment. For that purpose, the DMC will regularly review all incidences of serious adverse events, recurrent venous thromboembolic events and bleedings. Organizational aspects, responsibilities, and processes

will be described in the DMC charter. For further details see also Section 6.14.3 of the Integrated Protocol .

4.5 Data Rules

4.5.1 Baseline laboratory values

Hemoglobin (Hb), platelets, creatinine, alanine aminotransferase (ALT), total and direct bilirubin prior to Visit 2 will be considered for the baseline. If a blood creatinine value is not available up to IxRS assignment, the value from the sample taken no later than 14 days after IxRS assignment will be considered. In case of more than one available lab value the non-missing value closest to IxRS assignment will be taken. If the estimated glomerular filtration rate (eGFR) was not calculated then it will be calculated depending on the blood creatinine measurement method with original Schwartz formula or with the updated Schwartz formula as given in the Integrated Protocol Appendix 17.2 if all other required measurements (gender, age, height) are available. For patients from Japan the formula recommended by the Japanese Society for Pediatric Nephrology will be used as given in the Local Protocol Amendment 2 for Japan.

As in this study there is no pre-dose PD sampling at Day 1, the 10-16 hr post dose PD value at Visit 4 will be used as comparison/reference value per subject.

4.5.2 Compliance

4.5.2.1 Rivaroxaban

Overall compliance will be calculated for the actual treatment period (final stop date minus start date + 1 day) as total volume of suspension taken divided by the total volume of suspension to be taken considering required dose (volume) given the weight of the child and b.i.d. regimen between the first intake and last intake dates in the main treatment period. The total volume of suspension taken will be derived as the sum of amount taken for each bottle dispensed. The amount administered from a bottle will be calculated as the difference between the dispensed and returned amount. If the difference would be negative then the amount administered will be 0 (the volume dispensed could be larger as nominal 45 mL). If the volume returned is missing, but the investigator stated in the CRF that the patient took all medications not returned then the amount of taken will be the amount of dispensed. If the amount administered is also given then this will be considered. If the volume of dispensation taken by the patient cannot be determined for a bottle, because no bottle is returned and the amount administered is not stated, it will be assumed that the prescribed amount of study medication has been taken from the bottle unless the investigator commented it explicitly as non-compliance.

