5.1 Assignment of analysis sets

Final decisions regarding the assignment of subjects to analysis sets will be made during the review of study data and documented in the final list of important deviations, validity findings and assignment to analysis set(s) (see Section 4.6).

Full analysis set: This analysis set will include all enrolled children (except screening failures).

Safety analysis set: This analysis set will include all enrolled children who received at least one dose of study medication.

Per protocol set: This population includes all enrolled children who had at least 25 days study treatment. Children who discontinued study treatment earlier than 25 days due to an efficacy or bleeding outcome or due to death or due to a procedure defined in the study protocol or withdrew consent will not be excluded from the per protocol set. Children with a calculated compliance less than 50% will be excluded from the per protocol set, calculated

compliance between 50% and less than 80% and greater than 120% is considered as minor protocol deviation. These definitions are considered as clarifications to the definitions in the study protocol. The per protocol set may also exclude other major protocol deviations. Further details will be specified in the in the Protocol Deviation Document and in the Validity Review Report.

In addition to the analysis population defined in the study protocol, the following population will be used as well.

All subjects with at least 1 PK sample in accordance with the PK sampling strategy will be included in the PK analysis (PK analysis set).

All subjects with at least 1 blood sample for clotting parameters in accordance with the PD sampling strategy will be included in the PD analysis (PD analysis set).

Listing only set: This population includes all screening failures.

6. Statistical Methodology

Treatment groups will be displayed as study medication administered.

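### Rivaroxaban compliance appears to subtract a measured return from a nominal 45 mL fill, so used, overfilled bottles scored by subtraction understate intake and can shift the 80% and 120% deviation flags

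*SAP*

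**What the plan says.** SAP 4.5.2.1 defines overall compliance as total volume taken divided by total volume required for the child's weight and the twice-daily regimen. The numerator is summed over bottles, under four rules:

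- **Subtraction (the default).** "The amount administered from a bottle will be calculated as the difference between the dispensed and returned amount". A floor follows: "If the difference would be negative then the amount administered will be 0 (the volume dispensed could be larger as nominal 45 mL".
- **Return missing, investigator says all was taken.** If "the patient took all medications not returned then the amount of taken will be the amount of dispensed".
- **Recorded amount.** "If the amount administered is also given then this will be considered".
- **No bottle returned, no amount stated.** Here "it will be assumed that the prescribed amount of study medication has been taken from the bottle", unless the investigator has commented on non-compliance.

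Protocol 5.8.1 has the remaining suspension measured. SAP 5.1 excludes a child below 50% from the per protocol set, and states that "calculated compliance between 50% and less than 80% and greater than 120% is considered as minor protocol deviation". SAP 6.5.1.2 tabulates compliance as missing, below 50%, 50% to below 80%, and 80% or more.

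**The concern.** The floor comes with a reason: "the volume dispensed could be larger as nominal 45 mL". Overfill can make dispensed minus returned negative only if the dispensed figure is the nominal fill. If the actual fill were entered, a full bottle returned untouched would give zero.

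On that reading the same mismatch is present in used bottles. A bottle that held 50 mL and comes back with 5 mL supplied 45 mL but is scored as 40 mL. The floor corrects only the case that shows itself as a negative number. The error always runs downward and repeats with each bottle scored this way.

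The rules are also uneven. A family that returns its overfilled bottles is scored low, while a family that returns nothing and has no amount recorded is credited with the prescribed amount.

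At stake are the compliance table, the two minor-deviation flags and the detection of over-use. The table has no category above 80%, so the flag above 120% is the only place in these rules where over-use would appear. With 20 children planned, 10 per age group, one misplaced child is 1/20 = 5 percentage points of the overall table and 1/10 = 10 points of a cohort table.

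**Working it through.** The documents give no compliance result, overfill size or bottle count, so there is no figure of the plan's own to reproduce.

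**Inputs from the documents**
- Nominal fill 45 mL (SAP 4.5.2.1).
- Concentration 1 mg/mL (Protocol 5.4.1), so mg equals mL.
- Doses of 0.7 to 7.5 mg twice daily, i.e. 1.4 to 15.0 mL per day (Protocol Table 5-1).
- Treatment for 30 days (Protocol 5.3). No dose is taken on the day of Visit 4 (Protocol 6.4), so 29 days of intake is also plausible.

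**Assumptions**
- Overfill o of 1, 3 or 5 mL, the same in every bottle.
- All bottles scored by subtraction and returns measured exactly.
- Each bottle emptied before the next is opened.

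**Error per bottle.** True fill is 45 + o, the return is R, and true intake is T = 45 + o − R. The SAP value is max(0, 45 − R) = max(0, T − o). The understatement is therefore min(T, o).

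With a 50 mL fill (o = 5):

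| Returned (mL) | True intake | SAP value | Understated by |
|---|---|---|---|
| 50 | 0 | 0 | 0 |
| 47 | 3 | 0 | 3 |
| 5 | 45 | 40 | 5 |
| 5, with 45 recorded as administered | 45 | 45 | 0 |
| 0 | 50 | 45 | 5 |

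**Ceiling on the score.** T cannot exceed 45 + o, so T − o is at most T × 45/(45 + o). A child with true compliance c scores at most c × 45/(45 + o), however the bottles are used, provided all are scored by subtraction.
- c = 100%: 45/46 = 97.8% at 1 mL, 45/48 = 93.8% at 3 mL, 45/50 = 90.0% at 5 mL.
- c = 85%: 85 × 45/48 = 79.7% at 3 mL. The ceiling passes below 80% once o exceeds 45 × (85/80 − 1) = 2.8 mL.
- c = 125%: 125 × 45/48 = 117.2% at 3 mL. The ceiling passes below 120% once o exceeds 45 × (125/120 − 1) = 1.9 mL.

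**Lowest scores across the Table 5-1 doses, bottles emptied in turn**
- c = 100%, 1 mL: 0.9 mL dose, 29 days, 2 × 0.9 × 29 = 52.2 mL required, two bottles. (52.2 − 2)/52.2 = 96.2%.
- c = 100%, 3 mL: same child. First bottle 48 mL scored 45, second 4.2 mL scored 1.2. 46.2/52.2 = 88.5%.
- c = 100%, 5 mL: 0.9 mL dose, 30 days, 54 mL required. First bottle 50 mL scored 45, second 4 mL scored 0. 45/54 = 83.3%.
- c = 85%, 3 mL: 0.7 mL dose, 29 days, 40.6 mL required, 34.5 mL taken from one bottle. (34.5 − 3)/40.6 = 77.6%.
- c = 125%, 3 mL: 0.7 mL dose, 30 days, 42 mL required, 52.5 mL taken. (45 + 1.5)/42 = 110.7%.

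**Resulting ranges**

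| True compliance | Overfill (mL) | Calculated compliance |
|---|---|---|
| 100% | 1 | 96.2 to 97.8% |
| 100% | 3 | 88.5 to 93.8% |
| 100% | 5 | 83.3 to 90.0% |
| 85% | 3 | 77.6 to 79.7% |
| 125% | 3 | 110.7 to 117.2% |

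**A mid-range dose.** For 4.0 mL twice daily over 30 days, 240 mL is required. At 5 mL overfill this takes four bottles of 50 mL and 40 mL from a fifth: (4 × 45 + 35)/240 = 89.6%.

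**Overfill that moves a fully compliant child below 80%**
- Emptied in turn: more than about 8.1 mL in the most sensitive bands (0.2 × 40.6 = 8.1).
- Use spread evenly over the fewest nominal bottles, 30 days: more than 5.4 mL (0.2 × 54/2) to 9.0 mL (0.2 × 450/10).
- Two bottles more than the fewest, evenly used: more than 2.7 mL (0.2 × 54/4) to 7.5 mL (0.2 × 450/12).

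**Overfill that moves a fully compliant child below 50%**, evenly used fewest bottles: more than 13.5 mL (0.5 × 54/2) to 22.5 mL (0.5 × 450/10).

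**The case against.** The SAP never says outright that 45 mL is entered as the dispensed volume. This is an inference from its reason for the floor. It stands, because that reason has no other coherent meaning, but it remains an inference.

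A reader might infer that intake is understated for every overfilled bottle. The text does not support that. The floor scores an unused bottle correctly at 0, and the recorded-amount and assumed-amount rules do not rely on the subtraction. How many bottles fall under each rule is unknown.

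A reader might also infer that fully compliant children will drop below 80%. With bottles emptied in turn, none does at 1 to 5 mL of overfill. Even a child truly at 92% with 5 mL stays at about 80 to 83%. This must be worked with 50 mL bottles; counting bottles at 45 mL would use too many and overstate the loss. Opening spare bottles lowers the threshold, but the documents do not describe that pattern.

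The consequences are modest. Between 50% and 80% a child has only a minor deviation and a different table row. The 50% exclusion is out of reach for a well-compliant child. It could matter for one already near the line (truly 52% with 3 mL: at most 52 × 45/48 = 48.8%), and then only for the supportive per protocol analyses and the per protocol summary of treatment duration. Bleeding is analysed on the safety set and main efficacy on the full analysis set (SAP 6.2 and 6.3).

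Finally, Protocol 5.5 promises records of batch numbers, expiry dates and labels, not fill volumes. The sponsor would have to confirm that fill data exist. All of these points limit the concern; none removes the error for a used bottle scored by subtraction.

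**Conclusion.** The point holds in a limited form. For each used, overfilled bottle scored by subtraction, or emptied and scored as all taken, the SAP rule understates intake by min(amount taken, overfill), and the floor is exactly right only for an unused bottle.

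The size depends on an overfill that the documents do not give. Under the stated assumptions it is about 2 to 4 percentage points for a fully compliant child at 1 mL, 6 to 12 at 3 mL and 10 to 17 at 5 mL. Two results hold for any pattern of bottle use if all bottles are scored by subtraction: above 2.8 mL a child truly at 85% is flagged as below 80%, and above 1.9 mL a child truly at 125% escapes the flag above 120%. For an anticoagulant in young children, masked over-use is the more important of the two.

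The documents do not support reading this as a threat to the primary or main efficacy results. It is a small, correctable bias in a descriptive measure and its deviation flags.

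**What to change.** In SAP 4.5.2.1, state where the dispensed volume comes from. If the sponsor has the actual or mean fill of each released batch, use that in both the subtraction and the all-taken rule.

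If fill data are not available, keep the per-bottle floor at nominal fill, and report compliance and the 50%, 80% and 120% classifications at both nominal and maximum fill. In either case, give the number of bottles handled by each of the four rules.

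Signed differences should not be summed across bottles while the nominal fill is in use. Each unused overfilled bottle would then subtract its overfill from real intake elsewhere, which the floor prevents.

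The cost is one look-up value per batch or one extra display, plus a wording edit to a section that SAP version 2.0 had already reworked. No new data are needed from the children.
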